For patients with qualifying bleeding (rated on initial evaluation as at least “mild”) who have been randomized to receive Surgicel Snow, a single thin layer of dry Surgicel Snow will be applied over the area of bleeding and positioned firmly in direct contact to the areas of bleeding with blunt surgical instruments. Surgicel Snow will be left in the cavity to be absorbed. Dry gauze will not be placed over the material. No adjuncts will be added to enhance hemostasis, but patients with small arteriolar bleeding will have pressure maintained on the bleeding site for 60 seconds. Control patients will be managed with direct compression with gauze pads or laparotomy pads for four minutes. If hemostasis is not achieved by compression after four minutes, the source and rate of bleeding will be reevaluated and management will be determined by the surgeon. If the surgeon uses Surgicel Snow to achieve hemostasis at some point after 4 minutes, the patient will be included in the control group, but his/her data will be and flagged for the analysis.

Hemostasis will be defined as the absence of free-flow bleeding, specified as no new appearance of blood from the bleeding site. Pinpoint or petechial bleeding that appears but does not grow, or saturation of blood into the hemostat that may have occurred prior to or during the application of hemostatic agent that did not spread during the observation period, will not be considered free-flow bleeding. Control and treatment patients who do

[figure not shown]
not require a topical agent to achieve hemostasis, thus not requiring a bleeding evaluation will be excluded from the study.

For control patients, hemostasis failures at 4 minutes will be managed as per judgment of the primary surgeon, most likely be the use of a topical sealant. For treatment patients, hemostatic failure at 4 minutes will be reassessed for rate of blood loss and if the rate of loss is estimated at less than 25 cc per minute, additional observations will be made at 7 and 10 minutes. If failure of hemostasis at 4 minutes with an estimated loss of ≥ 25 cc/min, patient will be managed as per judgment of surgeon. Persistent bleeding at the 10 minute observation point will be treated as per the surgeon's judgment. The nature of the bleeding will be recorded throughout the study.

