Follow-up visits at 2 weeks (+/- 1 week) and 6 weeks (+/- 1 week) will be scheduled to determine if the patient has had a symptomatic collection or pelvic abscess. All subsequent procedures will be recorded, particularly those to manage bleeding.

The physician will take the time to describe the potential risks and benefits of the study as outlined in the consent form, to the patient. This will be reiterated by the assigned research coordinator. Only patients who have signed appropriate consent forms will be included in the study. Trained coordinators will be used and all standard safety protocols of the Clinical Research Department will be followed. The trained research coordinators will collect data at time of surgery. Should there be an adverse event, this will be documented and reported to the Principal Investigator (PI) and the IRB.

Intraoperative Flow Diagram

Selection and withdrawal of subjects:

Inclusion criteria:

1. Women ≥ 18 years of age
2. Women scheduled for standard multiport laparoscopic, single site laparoscopic, and robotic assisted laparoscopic hysterectomy.
2. Sites of surgery include Norwalk Hospital and Danbury Hospital.
3. Indication for surgery includes benign, complex benign, and malignant conditions.
4. Signed informed consent

Exclusion criteria:

1. Vaginal hysterectomy or open abdominal hysterectomy;
2. Congenital or acquired coagulation disorder including recent (within 7 days of surgery) therapeutic anticoagulation or use agents affecting platelet function, other than low dose aspirin. (Preoperative prophylactic heparin is not an exclusion criterion.)
3. Hysterectomy at the time of sacrocolpopexy.
4. Ovarian cancer

Participants may be withdrawn from the study at their request. Should a participant choose to withdraw from the study, no further clinical data will be collected on that patient and there will be no subsequent follow-up. In the event that a participant chooses to withdraw from the study, an additional study participant may be recruited to replace her.

Treatment of subjects:

Participants may continue all regular medications before and during the study.

The consent process will be incorporated into the consult visit prior to surgery.

Assessment of Efficacy:

The proposed clinical endpoints are time to hemostasis and failure to achieve hemostasis.

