Because multiple factors other than retroperitoneal bleeding contribute to the total intraoperative blood loss, we believe that the intraoperative estimated blood loss is not a pure indicator of the efficacy of a topical hemostatic agent for control of retroperitoneal bleeding. The determination of the primary endpoint of time to hemostasis is based upon a modification of the methods used by Hutchinson, et al in Cellulose (15). Secondary endpoints will include total operative time, intraoperative blood loss, blood transfusion, postoperative hemoglobin decrease, rate of postoperative symptomatic fluid collection,

postoperative pelvic abscess, and total cost for care from day of operation until six week (+/- 1 week) postoperative visit.

Assessment of Safety:

Whereas Surgicel Snow is generally used for minimal to mild bleeding from focal or widespread sources, should there be an adverse event related to the study conduction, this will be documented and reported to the study's PI. The PI will evaluate whether the adverse event involves risk to participants or others. If so, the PI may choose to change the protocol, change the consent form, require that all participants already enrolled be notified and/or re-consented, or suspend or terminate the study.

Statistical Analysis:

All data will be collected in paper format and transferred to an electronic database where all PHI will be removed and replaced with a study number. After conducting descriptive analyses, we will compare the treatment and control group on the primary and secondary outcomes. Multivariate analyses will be used to control for any observed variation between the study groups. Statistical significance will be assessed at $p < 0.05$.

It is anticipated that 60 participants will be enrolled in this study. The study will be terminated once all patients have completed their 6 week (+/- 1 week) follow-up post-surgery.

Direct Access to Source Data Documents:

The study's data collection sheet outlines when each data point will be collected. The study's PI, primary study coordinator, and co-authors will have access to all study data. These data will be used for study purposes only, and will be stored on a password-

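### Time to hemostasis cannot be read below 4 minutes in the control arm but could be in the Surgicel arm; if it is, the primary comparison is biased toward Surgicel

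*Combined protocol and SAP*

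**What the plan says.** Assessment of Efficacy gives the endpoints: "The proposed clinical endpoints are time to hemostasis and failure to achieve hemostasis". It then makes the first of these primary: "The determination of the primary endpoint of time to hemostasis is based upon a modification of the methods used by" a cited study. The modification is not described.

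The Design section defines hemostasis visually, as no fresh blood emerging at the bleeding site, and sets out the handling of each arm:

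- **Control.** "Control patients will be managed with direct compression with gauze pads or laparotomy pads for four minutes". The only assessment described comes afterwards: "If hemostasis is not achieved by compression after four minutes, the source and rate of bleeding will be reevaluated". Failures then pass to the surgeon's judgment, with no further scheduled reading.
- **Surgicel.** "Dry gauze will not be placed over the material". The one exception to an unpressed site is that "patients with small arteriolar bleeding will have pressure maintained on the bleeding site for 60 seconds". The first named reading is at 4 minutes: "For treatment patients, hemostatic failure at 4 minutes will be reassessed for rate of blood loss". If the loss is below 25 cc per minute, "additional observations will be made at 7 and 10 minutes".

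The same section states that the trial is unblinded, with 30 patients per arm. Statistical Analysis gives a 0.05 significance level. It names no test for the primary endpoint and no rule for tied or censored times.

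**The concern.** A visual endpoint can be timed only while the site can be seen. In the control arm it is hidden for the first four minutes. A bleed that stops at 1 minute and one that stops at 3.5 minutes both become known at 4 minutes. In the Surgicel arm the site can be watched from application, or from about 1 minute where pressure is held.

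The readable text does not say whether staff use that opportunity. It gives no clock start and no reading schedule before 4 minutes. If they do use it, control times have a 4-minute floor that Surgicel times lack, and the trial could report faster hemostasis that reflects only how long the control pads were held. With no blinding, nothing in the procedure offsets this.

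**Working it through.** **Inputs from the plan:** 30 per arm, significance level 0.05, control first read at 4 minutes, Surgicel readings named at 4, 7 and 10 minutes.

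**Assumptions, not in the plan:** exponential time to hemostasis with the same median in both arms (1, 2, 3, 4 or 6 minutes), a two-sided test, and all 30 per arm analyzed. The plan states no effect size, event rate or power, so there is no figure of its own to reproduce.

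**Step 1: why the floor matters.** Let p be the probability of hemostasis by 4 minutes, equal in both arms. Suppose Surgicel successes are timed when bleeding stops, control successes are recorded at 4, and failures at 4 minutes rank last and tie. For a random Surgicel–control pair:

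- Surgicel ranks better whenever it succeeds: probability p.
- Control ranks better only when it succeeds and Surgicel fails: p(1 − p).
- Net advantage to Surgicel: p − p(1 − p) = p².

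With no true difference this should be zero. If both arms are first read at 4 minutes, each ranks better with probability p(1 − p), and the net is zero.

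For exponential times, p = 1 − 0.5^(4/median). A 2-minute median gives p = 1 − 0.5² = 0.75 and a net advantage of 0.75² = 0.56.

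**Step 2: false-positive rates by simulation, equal true speed, 30 per arm.**

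| True median (min) | p | p² | Rank test, Surgicel timed early | Log-rank, Surgicel timed early |
|---|---|---|---|---|
| 1 | 0.94 | 0.88 | 100% | 100% |
| 2 | 0.75 | 0.56 | 97% | 93% |
| 3 | 0.60 | 0.36 | 72% | 60% |
| 4 | 0.50 | 0.25 | 43% | 32% |
| 6 | 0.37 | 0.14 | 20% | 11% |

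The rank test puts 4-minute failures last in both arms. The log-rank version uses the 7 and 10 minute Surgicel readings and censors control failures at 4 minutes; nearly all its rejections favor Surgicel.

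At medians of 1, 2 and 3 minutes the apparent gain in median time is 4 − 1 = 3, 4 − 2 = 2 and 4 − 3 = 1 minute, all from the floor.

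**Step 3: does the 60-second pressure help?** Hiding every Surgicel site for the first minute, which is more than the plan does, gives log-rank rates of 100%, 93%, 59%, 32% and 11%. The result is almost unchanged.

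**Step 4: the other reading of the text.** If Surgicel is also first read at 4 minutes, false rejection is about 3% to 5% with no tilt toward Surgicel. Fisher's exact test on status at 4 minutes gives 0.2%, 2.7% and 3.2% at medians of 1, 2 and 3 minutes.

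**Step 5: fewer analyzed.** With early Surgicel timing and a 2-minute median, the log-rank rate is 70% at 15 per arm and 56% at 10 per arm.

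**The case against.** A reader might infer that the primary comparison necessarily favors Surgicel. The documents do not support that. The bias needs Surgicel readings before 4 minutes, and the text never says they are taken; 4 minutes is the first named reading in both arms. On that schedule the bias is absent. This part of the objection stands, and the conclusion has to be conditional.

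A reader might also infer that no time could be derived if both arms are first read at 4 minutes. That too goes too far, because Surgicel successes can fall at 4, 7 or 10 minutes. Control has no matching later readings, however, so this coarse time cannot be compared between arms beyond 4 minutes.

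The intraoperative flow diagram is not reproduced here. The data collection sheet, which Direct Access to Source Data Documents says sets out when each item is collected, is not among the documents, and neither is the cited timing method. Any of these may fix reading times, and their absence here is not a fault in the plan. They could settle whether Surgicel is read early, but no schedule makes a compressed site visible.

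The size also depends on unstated medians and on the number analyzed. Patients who need no topical agent are excluded, and the Background says retroperitoneal bleeding occurs in a minority of procedures, so fewer than 30 per arm may contribute. The rates are lower with longer medians and smaller groups. That limits the size, not the mechanism.

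**Conclusion.** The concern holds in conditional form. The 4-minute floor in the control arm follows from the text, and the Surgicel arm has no equivalent. A plain comparison of times then fails in one of two ways:

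- **Surgicel timed before 4 minutes:** the comparison is biased toward Surgicel at equal true speed. False-positive rates run from about 100% (median 1 minute) to 20% (median 6 minutes) with a rank test, and from 100% to 11% with a log-rank test.
- **Both arms first read at 4 minutes:** there is no such bias, but up to 4 minutes the primary endpoint is a yes/no result labeled as a time, and later readings exist in one arm only.

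The text does not say which applies. The rates rest on exponential times, assumed medians and 30 analyzed per arm. The direction does not depend on the exponential form: under the ranking in step 1, the net advantage p² is positive whenever any hemostasis occurs by 4 minutes.

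**What to change.** In Design and Assessment of Efficacy, state when the clock starts in each arm and set a common first assessment at 4 minutes for both.

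In Statistical Analysis, treat every success by 4 minutes alike in the between-arm primary comparison, as interval-censored between 0 and 4 minutes. Because control has no scheduled reading after 4 minutes, this is equivalent to comparing hemostasis yes/no at 4 minutes, which builds on the failure endpoint the plan already names. Report any Surgicel times below 4 minutes, and the 7 and 10 minute readings, descriptively for that arm only. Check the flow diagram and data collection sheet for consistency with this.

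The change is to protocol and analysis wording; neither arm's treatment is altered. The cost is information: early Surgicel times no longer count in the comparison. At 30 per arm, Fisher's exact test has about 44% power for 75% versus 95% and about 30% for 60% versus 80% (assumed rates). The sponsor should accept that limit knowingly.

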from the development of the pelvic retroperitoneal space is generally minimal and frequently, but not always, requires no specific hemostatic measures. Bleeding from mobilization or excision of retroperitoneal structures, such as during lymphadenectomy and dissection of cervical or intra-ligamental leiomyoma, has a greater propensity for blood loss and will frequently require standard hemostatic measures such as vascular clips, suture ligation, or electrosurgical methods for control. Although retroperitoneal bleeding occurs in a minority of the proposed procedures, the nature of bleeding within the retroperitoneal space is similar among the three procedures proposed.

The results of extensive bleeding in the retroperitoneal spaces include significant blood loss with dissection along the extraperitoneal fascial planes, as well as intraperitoneal collection, hematoma, and abscess. Patients with postoperative pelvic collections may present with symptoms of fever, rectal pain, or lower abdominal pain (13). Treatment often requires IR (interventional radiology) drainage and readmission for inpatient parenteral antibiotic therapy. The initial approach to hemostasis in the pelvis depends on the nature of bleeding encountered. When bleeding is encountered during pelvic dissection, evaluation of the extent and sources of bleeding, as well as its anatomic location and proximity to vital structures are the first requirements. The process of evaluating bleeding requires inspection of the bleeding sites augmented by irrigation, suctioning, and blotting with gauze. Through this process, the rate (minimal, mild, moderate, and severe)¹, distribution

¹ Estimated as blood loss in 10 second observation time as follows

1. minimal less than 2 cc
2. mild 2-3 cc
3. moderate 3-5 cc
4. severe ≥ 5

(local vs. diffuse), anatomic site (i.e., if in close proximity to vital structures), and source of blood loss (small arterial, venous or capillary) is ascertained.

Objectives:

This study would examine the efficacy of Surgicel Snow vs. direct compression in the control of capillary, venous, and small arterial hemorrhage when ligation or other conventional methods of control are impractical or ineffective in patients undergoing laparoscopic or robotic assisted laparoscopic hysterectomy. The intraoperative inclusion bleeding characteristics are minimal and mild retroperitoneal bleeding and moderate retroperitoneal bleeding that has been adequately reduced by standard surgical methods.

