
Design:

The proposed research method will use a randomized, concurrent control, no blinding. We are limiting our study to retroperitoneal dissection hysterectomy only to control for the expected variation in bleeding among the potential procedures. We propose to randomize 60 patients - 30 to the treatment group and 30 to the control group. The patients participating in this study would be patients scheduled for hysterectomy at Norwalk Hospital and Danbury Hospital under the direction of [name], [name], and [name].

The patient population is drawn from throughout the State of Connecticut. Indications for hysterectomy will include benign, complex benign uterine and adnexal pathology, as well as gynecologic oncology cases. Vaginal hysterectomy procedures and open abdominal procedures will be excluded. Complex benign pathologies are those that are likely to require retroperitoneal dissection and or ureterolysis, (e.g., cervical leiomyoma, endometriosis, etc.

Peritoneal access for hysterectomy will include open laparotomy, standard multiport laparoscopy, and robotic assisted laparoscopy. All patients scheduled for indicated procedures will be screened for inclusion. Once consented, patients will be randomized to the control group or the treatment group. The control group will receive standard of care, and the treatment group will receive Surgicel Snow. A random number generator will be used to determine test vs. control in blocks of 10.

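### Patients are randomized at consent without blinding and some are then excluded on a bleeding judgment during surgery, with no stated concealment of the arm until grading and no count of exclusions by arm

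*Combined protocol and SAP*

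**What the plan says.** The order of events has to be assembled from several sections of the combined protocol and SAP.

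- **Consent** (Treatment of subjects): "The consent process will be incorporated into the consult visit prior to surgery".
- **Randomization** (Design): "Once consented, patients will be randomized to the control group or the treatment group". It therefore precedes any observation of bleeding.
- **Blinding** (Design): "The proposed research method will use a randomized, concurrent control, no blinding".
- **Size and list** (Design): "We propose to randomize 60 patients - 30 to the treatment group and 30 to the control group"; "A random number generator will be used to determine test vs. control in blocks of 10".
- **Exclusion** (Design, intraoperative management): control and treatment patients who do "not require a topical agent to achieve hemostasis, thus not requiring a bleeding evaluation will be excluded from the study".
- **Entry threshold**: the same part of Design sets qualifying bleeding at mild or worse. Objectives says "The intraoperative inclusion bleeding characteristics are minimal and mild retroperitoneal bleeding", and adds moderate bleeding already reduced by standard methods. By the Background footnote, the grade is an estimate of blood loss over 10 seconds, with minimal below 2 cc and mild from 2 cc.

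The plan has some safeguards. The exclusion is worded for both arms. Design has the bleeding characteristics recorded and keeps controls who later receive the product in the control group, flagged. Statistical Analysis plans descriptive analyses and multivariate adjustment for observed differences. It does not name bleeding grade as a covariate, define an analysis set, or call for exclusions to be tabulated by arm.

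**The concern.** Randomization makes the arms comparable as randomized. The primary comparison uses only those who remain after a judgment made during surgery, in an open-label trial, after assignment. If that judgment is independent of the arm, the remaining groups are still comparable. If the arm influences it, they are not, and time to hemostasis differs between arms even when the product does nothing. The bias could favor either arm.

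Three features leave room for influence. The grade is a visual estimate with a border at 2 cc. Objectives and Design disagree on whether minimal bleeding qualifies. The exclusion also turns on whether a topical agent is needed, which is the treatment under study. Read literally, a control whose bleeding stops under compression did not need one. The rest of the sentence suggests an earlier judgment, but the rule should not depend on interpretation.

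That the surgeon knows the arm when grading is an inference from the order of events and the absence of blinding. The text does not state it.

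**Working it through.** **1. The plan's own figure.** The sample size of 60 (30 per arm) cannot be reproduced, because no effect size, standard deviation or power is given. The working below shows only what arm-dependent retention could do.

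**2. Assumed inputs.** None of these is in the documents. Bleeds are 40% minimal, 40% mild and 20% moderate. Hemostasis by 4 minutes is 95%, 75% and 50% respectively. There is no treatment effect.

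**3. Direct arithmetic on 4-minute hemostasis.**

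- All minimal bleeds kept: 0.4×0.95 + 0.4×0.75 + 0.2×0.50 = 0.780.
- Half kept: (0.2×0.95 + 0.4×0.75 + 0.2×0.50)/0.8 = 0.59/0.8 = 0.7375.
- None kept: (0.4×0.75 + 0.2×0.50)/0.6 = 0.40/0.6 = 0.667.

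The corresponding median times are 1.61, 1.89 and 2.47 minutes. These gaps come from selection alone.

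**4. Type I error.** The method was 20,000 simulated trials per case. Times are exponential within grade, matched to the 4-minute rates and capped at 10 minutes. Equal numbers of bleeding patients are drawn per arm and retention is then applied. The test is a two-sided rank-sum at 0.05, unadjusted and stratified by recorded grade (van Elteren).

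| Retention in the two arms | Kept, of 30 bleeding per arm | Unadjusted | Stratified |
|---|---|---|---|
| Same cut-off | equal | 4.9% | 4.9% |
| All vs half of minimal bleeds | 30 vs 24 | 6.7% | 5.0% |
| All vs none (extreme) | 30 vs 18 | 17.8% | 4.9% |
| One arm records a quarter of its minimal bleeds as mild, the other excludes all | 21 vs 18 | 6.4% | 5.8% |
| As above, half | 24 vs 18 | 9.6% | 7.8% |
| As above, all (extreme) | 30 vs 18 | 18.1% | 11.9% |

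With 15 bleeding patients per arm the unadjusted figures are 5.8% (all vs half), 10.5% (all vs none) and 6.6% (half regraded; 5.9% stratified).

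**5. Why stratification fails in the last three rows.** The recorded-mild stratum then holds different patients in each arm. True 4-minute success in it is 0.75 with no regrading, but (0.2×0.95 + 0.4×0.75)/0.6 = 0.817 with half of the minimal bleeds regraded, and (0.4×0.95 + 0.4×0.75)/0.8 = 0.85 with all.

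**6. A second model.** Let the outcome correlate ρ with latent severity, and let each arm keep its most severe share q. The spurious difference is ρ[m(q₀) − m(q₁)], with m(q) = φ(z₁₋q)/q. For 40% of controls and 60% of treated patients kept, it is 0.161 SD at ρ = 0.5 and 0.225 SD at ρ = 0.7. Type I error (t-test) is 7.0% and 10.4% with 30 randomized per arm. With 40% against 50% kept and ρ from 0.3 to 0.7, it is 4.9% to 6.7%.

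**7. Losses.** Background says "Although retroperitoneal bleeding occurs in a minority of the proposed procedures", but Design narrows the trial to hysterectomy with retroperitoneal dissection, so the share here is not given. If an assumed 50% to 20% qualify, 60×0.5 = 30 down to 60×0.2 = 12 remain. Replacement (Selection and withdrawal of subjects) is stated only for patients who choose to withdraw.

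**8. Predictability.** If the list is tracked, a fixed 1:1 block of 10 makes 2×5/(5+1) = 1.67 assignments per block certain in advance. Known blocks of 4 or 6 would give 1.33 and 1.50. Shorter blocks alone do not help; the sizes must also be undisclosed.

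**The case against.** The central gap may lie in the record. The intraoperative flow diagram is not shown, and the gap falls in the middle of the exclusion sentence. Statistical Analysis is followed by a reference to a data collection sheet with the timing of each item, which is also not in the text. Either could give the order of grading and disclosure. The surgeon's knowledge of the arm is inferred, and the exclusion is worded alike for both arms. This stands as a limit on certainty.

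The simulation varies retention at the minimal/mild border, whereas the exclusion sentence concerns patients who are never graded. That is fair as a description. Both, however, are judgments made after assignment that decide who is compared.

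The inputs are invented, and 30 bleeding patients per arm supposes that all 60 bleed. With 6 per arm the error is 4.5% (all vs half) and 5.1% (half regraded). With times grouped at 4, 7 and 10 minutes and 30 per arm, it is 6.1% (all vs half), 7.6% (half regraded) and 14.4% (all vs none). Fisher's test on 4-minute success gives 4.1%, 5.2% and 10.8%. So the size is uncertain and often modest. But a rejection rate near 5% in a small sample partly reflects low power; the bias in the estimate does not shrink with it.

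Finally, recording and adjustment remove the problem when grading is correct. This is true, and it is the weaker of the two threats. Adjustment cannot repair a grade that itself depends on the arm, or severity differences within a grade.

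**Conclusion.** The concern holds. The text as it can be read places open-label assignment before an estimated, inconsistently defined entry judgment. It states no masking of the arm at that point, no analysis set covering those excluded and no accounting of them by arm.

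Its size cannot be fixed from the documents. It ranges from no bias under a common cut-off, through type I error of roughly 6% to 10% for partial arm-dependence, to about 18% unadjusted in the extremes, all under assumed grade mixes, hemostasis rates and retention. The direction is unknown. Confidence is medium, because the flow diagram is unseen and the surgeon's knowledge of the arm is inferred. The change is still needed: selection of this kind affects the primary endpoint and cannot be reliably undone at analysis, and prevention is cheap.

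**What to change.** Keep consent before surgery and move allocation to after grading.

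- Reconcile Objectives and Design into one definition of qualifying bleeding.
- In the operating room, have the coordinator record the grade and the time, and only then open the next concealed allocation (sealed opaque envelope or electronic).
- Replace fixed blocks of 10 with varied block sizes not disclosed to the surgeons.
- Replace the exclusion sentence with: *Consented patients with no qualifying bleeding recorded before allocation are not randomized.*
- State that every randomized patient is analyzed in the assigned arm, name recorded bleeding grade as a covariate in the primary analysis, and report how many consented patients were not randomized and why.

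If randomization must stay before surgery, the minimum is to hide the assignment until the grade is recorded and to report exclusions by arm and grade. That addresses the bias but not the losses.

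The cost is a protocol amendment, envelopes or an electronic system, and a short pause in surgery. Coordinators already collect data at surgery, so no staff are added. More women would be consented than randomized: 60/0.5 = 120 to 60/0.2 = 300 for 60 randomized, if an assumed 50% to 20% qualify. Reaching 60 patients with qualifying bleeding under the present order would take the same number of consents.

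### Patients are excluded after open randomisation according to whether they needed a topical agent, not on bleeding recorded before treatment, so the exclusion can fall differently on the two arms

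*Combined protocol and SAP*

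**What the plan says.** **Order of events.** Under Treatment of subjects: "The consent process will be incorporated into the consult visit prior to surgery". Under Design: "Once consented, patients will be randomized to the control group or the treatment group". Design also states: "The proposed research method will use a randomized, concurrent control, no blinding". Allocation therefore precedes any view of the bleeding, and nothing says when the surgeon learns it.

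**The exclusion.** Later in Design, control and treatment patients alike are removed if they do "not require a topical agent to achieve hemostasis, thus not requiring a bleeding evaluation will be excluded from the study". This rule is absent from the numbered criteria under Selection and withdrawal of subjects.

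**Qualifying bleeding.** It is described twice. Objectives says "The intraoperative inclusion bleeding characteristics are minimal and mild retroperitoneal bleeding", adds "moderate retroperitoneal bleeding that has been adequately reduced by standard surgical methods", and sets the question in the situation "when ligation or other conventional methods of control are impractical or ineffective". Design begins its Snow instruction with "For patients with qualifying bleeding (rated on initial evaluation as at least" and names the grade mild. The exclusion sentence cites neither description.

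**Treatment by arm.** Snow patients with qualifying bleeding have the product applied. Controls have four minutes of compression; if that fails, the surgeon decides, and a topical sealant is the expected choice. A control given Snow after four minutes stays in the control group and is flagged.

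**The concern.** Everyone removed by this rule has already been randomised. Such an exclusion is harmless if it depends only on facts fixed before treatment and judged without regard to arm. This one depends on whether an agent was needed, and need shows itself differently in each arm. For a Snow patient the agent is given by allocation, so the question hardly arises. For a control, need is most clearly shown by failure of compression, which is the outcome itself.

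A team that knows the arm can, in good faith, decide that a control whose bleeding stopped easily never needed an agent. Removing her takes a short time to hemostasis out of the control arm only. Control times then look longer and control success lower, with no true difference. Time to hemostasis is the primary endpoint and failure of hemostasis the other efficacy endpoint, so the distortion falls directly on the main result.

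**Working it through.** **1. The plan's own figures.** 60 patients, 30 per arm, in 6 blocks of 10 (6 × 10 = 60). No effect size, standard deviation, hemostasis rate or expected number of exclusions is given, so there is no stated figure to reproduce. The size below is illustrative.

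**2. The criterion by arm, when bleeding qualifies.**

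| | Snow | Control |
|---|---|---|
| First treatment | Snow, by allocation | Compression, 4 minutes |
| When an agent is used | At once | Probably only after compression fails |
| Can easy hemostasis be read as no need for an agent? | Hardly, she has had it | Yes |

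The sentence also makes the missing bleeding evaluation a consequence of not needing an agent, rather than the test.

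**3. The two descriptions of qualifying bleeding.**

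| | Objectives | Design |
|---|---|---|
| Minimal bleeding | Included | Not included (mild or worse) |
| Moderate bleeding | Only once adequately reduced | No such condition |
| Conventional methods unsuitable | Part of the stated setting | Not repeated |
| Which rating counts | Implies after reduction, if moderate | Initial evaluation |

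Even a reader who ties the exclusion to qualifying bleeding has no single definition to apply.

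**4. Simulation of one-sided removal.** All inputs are assumed:
- Time T is exponential with the same distribution in both arms. P(T ≤ 4 min) = p = 0.6, so the rate is −ln(0.4)/4 = 0.229 per minute.
- Times are capped at 4 or 10 minutes; ranges span the two caps.
- There are n = 30 analysable patients per arm before removal.
- The k controls judged quickest are dropped. Judgement has correlation r with the normal score of true time.
- The test is a two-sided Wilcoxon at 0.05, with 40,000 runs per cell. The standard error near 5% is √(0.05 × 0.95/40,000) = 0.11 percentage points.

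| Controls dropped | r | False rejection | Of which favouring Snow | Observed control 4-min success |
|---|---|---|---|---|
| 0 | – | 4.8% | 2.4% | 60% |
| 3 | 0.3 | 5.1-5.2% | 3.6-3.7% | 58% |
| 3 | 0.5 | 6.3-6.4% | 5.2-5.4% | 57% |
| 3 | 1 | 10.9-11.4% | 10.3-10.7% | 56% |
| 6 | 0.3 | 6.3-6.6% | 5.3-5.5% | 56% |
| 6 | 0.5 | 9.3-9.5% | 8.8-8.9% | 54% |
| 6 | 1 | 24.2-26.0% | 24.0-25.9% | 50% |

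Hand check at r = 1: of 30 controls, 0.6 × 30 = 18 succeed. Dropping 3 successes gives 15/27 = 56%; dropping 6 gives 12/24 = 50%. Both match the table.

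**5. Sensitivity.**
- With p from 0.4 to 0.8 and r from 0.3 to 0.5, false rejection is 5.1-6.4% for 3 dropped and 6.0-9.5% for 6.
- Background says retroperitoneal bleeding occurs in a minority of procedures. If only 60 are randomised, fewer than 30 × 0.5 = 15 per arm may qualify. At n = 15, dropping 3 gives 5.2-6.6%, against 4.5-4.6% with none dropped.
- If judgement is unrelated to outcome (r = 0), dropping 3 or 6 controls leaves 4.6-4.9%.

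**6. Equal removal.** Dropping the same number from both arms (3 or 6 each, r 0.3-0.5, n = 30) gives 4.8-5.7%, with 2.4-2.9% favouring Snow. The directional bias comes from unequal application.

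**7. Literal reading, as an outer bound.** Suppose true 4-minute success is s in both arms and a fraction f of control successes is excluded. Observed control failure is (1 − s)/[(1 − s) + s(1 − f)]. At s = 0.7 and f = 0.5 this is 0.30/(0.30 + 0.35) = 46%, against a true 30%. Fisher's exact test (30 per arm, 20,000 runs) then rejects in 17.4% of trials, against 2.6% at f = 0. At f = 1 only 30 × 0.3 = 9 controls remain, all failures.

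**The case against.** The sentence names both arms, and its closing words suggest that the people meant are those with no bleeding to evaluate. A control who has had four minutes of compression plainly had bleeding to evaluate. The plan's provision for control failures at 4 minutes, and its failure endpoint, presuppose that control successes are kept. Design also already retains controls who later receive Snow. The flow diagram, not shown here, and the data collection sheet may set the order of steps. Finally, the magnitude rests on one-sided removal. If 6 controls and 3 Snow patients are dropped (r = 0.5, 10-minute cap, n = 30), false rejection is about 6.2%, with 4.7% favouring Snow, against about 9.5% in all when only controls are dropped.

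Much of this stands. The milder intent is likely, so the outer bound in step 7 should not be used to judge severity, and the retention of crossover controls deserves credit. But naming both arms does not make a test of need equal when allocation settles need in one arm and outcome can reveal it in the other. The written criterion remains a judgement that may be made with the arm known. A clearer diagram would help, but the sentence would still have to agree with it. The disagreement between Objectives and Design is a separate fault; it matters here because a repaired exclusion needs one definition to cite.

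**Conclusion.** The concern holds: the rule is wrong as written and should be fixed. It permits removal of randomised patients on a ground that can depend on arm and outcome, and the foreseeable direction favours Snow. Under modest judgement (r 0.3-0.5) and 3 to 6 controls dropped from 30, false results favouring Snow rise from 2.4% to about 4-9%, and the two-sided error reaches at most about 10%. Rates of 11-26% need perfect judgement. These sizes rest on assumed hemostasis rates, time distribution, test, number dropped and number analysable. The defect itself rests on the text. If the team in fact applies one pre-treatment standard to both arms, the directional bias disappears, but nothing in the plan requires that.

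**What to change.** Replace the exclusion sentence with text such as:

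> After randomisation a patient is excluded only if the record made before the assigned treatment starts shows that the qualifying-bleeding conditions were not met. The rule is applied identically in both arms; later need for or use of a topical agent plays no part. Every patient who met the conditions is analysed in her randomised arm, including controls who reach hemostasis by compression alone and controls later given Surgicel Snow. Exclusions are reported by arm, with the recorded grade and the condition not met.

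Reconcile Objectives and Design into one definition of qualifying bleeding. It must settle whether minimal bleeding qualifies, how the condition on conventional methods is recorded, and which recorded grade counts for moderate bleeding that has been reduced. The clinical choice belongs to the investigators. Put the definition with the numbered selection criteria and in the flow diagram. Where feasible, complete the assessment before the allocation is opened in theatre.

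**Cost.** One sentence and one reconciled definition. Bleeding is already rated at the initial evaluation and coordinators already collect data at surgery, so a timed entry adds little. Opening the allocation only after the assessment changes the present sequence slightly and needs a sealed or on-call step. Without it, the timed record limits discretion but does not remove it.
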